5.3 Lifestyle Considerations

The following lifestyle considerations apply for the trial.

5.3.1 Meals and Dietary Restrictions

Consumption of grapefruit, starfruit, Seville orange, and their processed products such as juices is prohibited from 3 days before Visit 2 until the end of the double-blind tapering period. Consumption of St. John's wort-containing foods is prohibited from Visit 2 through Visit 9.

5.3.2 Caffeine, Alcohol, and Tobacco

From Visit 2 through Visit 9, excessive caffeine consumption and smoking should be avoided, and consumption of alcoholic beverages should be avoided wherever possible.

5.3.3 Activity

Not applicable.

5.4 Screen Failures

A screen failure is a subject from whom informed consent is obtained and is documented in writing (ie, subject signs an informed consent form [ICF]), but who is not dispensed the IMP at Visit 2.

If the subject meets the definition of a screen failure in this trial, the following information will be recorded in the eCRF:

- Date of informed consent
- Visit date (screening visit)
- Demographics (collection date, birth date, sex, race, ethnicity, country)
- Result of eligibility assessment
- Screen failure date
- Reason for screen failure

Subjects who participate in the trial and subsequently become screen failures can undergo rescreening. When rescreening is performed, separate written consent needs to be obtained and a new subject ID will be assigned prior to the screening examination.

6 Trial Treatments

6.1 Trial Treatments Administered

For information regarding the dose regimen and treatment period, including any follow-up period(s) for each treatment group of the trial, see Section 6.1.1.

6.1.1 Dosage and Administration

6.1.1.1 Placebo Lead-in Period (Single-blind With Subjects Blinded to Treatment Received)

Two placebo tablets will be administered orally once daily for 1 week.

6.1.1.2 Double-blind Treatment Period

Placebo group

Two placebo tablets will be administered orally once daily for 6 weeks.

• OPC-64005 10-mg group

One placebo tablet and one OPC-64005 10-mg tablet will be administered orally once daily for 6 weeks.

• OPC-64005 20-mg group

One placebo tablet and one OPC-64005 10-mg tablet will be administered orally once daily for 1 week, followed by two OPC-64005 10-mg tablets for 5 weeks.

6.1.1.3 Double-blind Tapering Period

Placebo group

Two placebo tablets will be administered orally once daily for 1 week.

• OPC-64005 10-mg group

Two placebo tablets will be administered orally once daily for 1 week.

OPC-64005 20-mg group

One placebo tablet and one OPC-64005 10-mg tablet will be administered orally once daily for 1 week.

6.1.1.4 At Discontinuation

If discontinuation occurs during the period between the start of IMP administration after Visit 4 and the start of IMP administration after Visit 9, the IMP dose will be tapered (1 week [7 days \pm 2 days]) to the following regimens (however, if the investigator judges that the IMP needs to be discontinued due to an AE or if the IMP dose cannot be tapered due to the subject's circumstances such as he/she does not wish to taper the dose, dose tapering is not mandatory):

Placebo group

Two placebo tablets will be administered orally once daily for 1 week.

OPC-64005 10-mg group

Two placebo tablets will be administered orally once daily for 1 week.

OPC-64005 20-mg group

One placebo tablet and one OPC-64005 10-mg tablet will be administered orally once daily for 1 week.

If discontinuation occurs during the period between the start of IMP administration after Visit 3 and the start of IMP administration after Visit 4 or between the start of IMP administration after Visit 9 and Visit 10, dose tapering is not necessary. If the IMP dose is tapered after discontinuation, the IMP will be dispensed according to the instructions from the IRT system, as the IMP will be administered under double-blind conditions.

6.1.1.5 Handling of Missed Doses

If the subject realizes that he/she missed taking the IMP the day before, he/she will not take the missed IMP dose from the day before.

6.1.1.6 Investigation on Drug Compliance

The investigator will confirm the drug compliance status between the scheduled visits, and record the daily dose, treatment start date, and treatment end date in the source document and eCRF.

The drug compliance rate will be calculated by the following formula: [Dose (number of tablets) between the scheduled visits] / [number of prescription days between the scheduled visits \times 2 tablets] \times 100. If the drug compliance rate between the scheduled visits is < 65%, administration will be discontinued (see Section 7.3.3).

6.1.2 Medical Devices

Not applicable.

6.2 Management of Investigational Medicinal Product

For full details on IMP management, please refer to the OPC-64005 IB and a separate manual.

6.2.1 Packaging and Labeling

The IMP will be provided by the sponsor or designated agent to the IMP manager. The IMP will be supplied as blister cards. Each blister card used in the dosing period will be labeled to clearly disclose the subject ID, compound ID, protocol number, sponsor's name and address, route of administration, lot number, expiry date, and storage method, etc.

6.2.2 Storage

The IMP will be stored in a securely locked cabinet or enclosure. Access will be limited to the IMP manager.

The IMP will be stored according to the conditions indicated on the IMP label.

The trial site staff will maintain a temperature log in the IMP storage area to record the temperature.

6.2.3 Accountability

The IMP manager must maintain an inventory record of the IMP (investigational or placebo) received, dispensed, administered, and returned. The IMP manager may not provide the IMP to any patient not participating in this protocol.

6.2.4 Returns and Destruction

Upon completion or termination of the trial, all used IMP containers, unused IMP, and partially used IMP must be returned to the sponsor or a designated agent. All IMP returned to the sponsor must be accompanied by the appropriate documentation and be clearly identified by protocol number and trial site number on the outermost shipping container. Returned supplies should be in the original containers (eg, subject kits). The assigned trial monitor will facilitate the return of used IMP containers, unused IMP, and partially-used IMP.

6.2.5 Reporting of Product Quality Complaints

A Product Quality Complaint (PQC) is any written, electronic, or verbal communication by a healthcare professional, consumer, subject, medical representative, Competent Authority, regulatory agency, partner, affiliate or other third party that alleges deficiencies or dissatisfaction related to identity, quality, labeling, packaging, reliability, safety, durability, tampering, counterfeiting, theft, effectiveness, or performance of a drug product or medical device after it is released for distribution. Examples include, but are not limited to, communications involving:

- Failure of a product to meet any of its specifications
- Incorrect or missing labeling
- Packaging issues (eg, damaged, dirty, crushed, missing product)
- Blister defects (eg, missing, empty blisters)
- Product defect (eg., odor, chipped, broken, embossing illegible)
- Loss or theft of product

6.2.5.1 Eliciting and Reporting Product Quality Complaints

The investigator or designee must record all PQCs identified through any means from the receipt of the IMP from the sponsor or sponsor's designee, through and including reconciliation and up to destruction, including subject dosing. The investigator or designee must notify the sponsor or sponsor's designee by email (destination address: [contact]) of the information listed in Section 6.2.5.2 immediately after acknowledging the PQC.

Identification of a PQC by the subject should be reported to the site investigator, who should then follow the reporting mechanism above.

6.2.5.2 Information Required for Reporting Product Quality Complaints

• Description of complaint

- Reporter identification (eg, subject, investigator, site, etc.)
- Reporter contact information (eg, address, phone number, e-mail address)
- ID of material (product/compound name, kit number)
- Clinical protocol reference (number and/or trial name)
- Dosage form/strength (if known)
- Pictures (if available)
- Availability of complaint sample for return

6.2.5.3 Return Process in the Case of Product Quality Complaints

Indicate during the report of the PQC if the complaint sample is available for return. The sponsor may provide sample return instructions, when applicable.

It must be documented in the site accountability record that the complaint sample for a dispensed kit has been forwarded to the sponsor for complaint investigation.

6.2.5.4 Assessment/Evaluation

Assessment and evaluation of PQCs will be handled by the sponsor.

6.3 Measures to Minimize/Avoid Bias

This trial will be performed as a randomized double-blind trial to minimize bias.

Treatment assignment codes will not be disclosed to the subjects or investigator. Except for designated persons, the treatment assignment code will not be disclosed to the sponsor's trial staff including contract research organizations (CROs) (except for the bioanalytical laboratory and pharmacogenomic [PGx] laboratory) during the trial.

Emergency keys are controlled by the IRT system until the end of the trial. They will be disclosed according to the procedures for breaking the blind when a medical emergency occurs to a subject and it is judged important to identify the treatment assignment code for treatment of the subject. Procedures for breaking the blind can be found in Section 8.8.7.

If the IMP is collected by the sponsor before unblinding, the IMP will be collected in the sealed state.

Subjects will be assigned to the OPC-64005 10-mg group, OPC-64005 20-mg group, or placebo group at a ratio of 1:4:4 using the dynamic allocation method (minimization method). A separate specification will be developed to provide details.

Results of drug concentration measurement and PGx assessment should be retained in a manner that prevents their disclosure until unblinding at the end of the trial. These tests

will be performed by the specified laboratories, and will not be performed at a clinical laboratory of the trial site.

6.4 Subject Compliance

During the trial, subjects will be placed under the management of the investigator. The investigator will instruct subjects to adhere to the following:

- Subjects must adhere to the specified schedule during the trial
- The trial must be discontinued when the drug compliance rate between the scheduled visits is < 65%
- Subjects must practice appropriate contraceptive methods
- Subjects must adhere to the requirements in Section 5.3 and Section 6.5
- Subjects must not disclose information obtained as a result of participation in the trial to third parties
- If a rash develops on the skin after the start of IMP administration, subjects must immediately contact trial site staff and follow the investigator's instructions

6.5 Concomitant Medications or Therapies

The investigator will record all concomitant medications taken by the subject from 28 days prior to informed consent through Visit 10 and all concomitant therapies taken by the subject from 6 weeks prior to informed consent through Visit 10 in the eCRF. The investigator will also record all concomitant medications and therapies taken by the subject for treatment of an AE or which caused an AE until the end of the trial (defined as the date of last observation or date of final contact attempt) in the eCRF.

For concomitant medications, the following will be recorded in the eCRF: medication, indication, dose, frequency, route, start date and end date. For concomitant therapy, the following will be recorded in the eCRF: therapy, indication, start date and end date.

6.5.1 Prohibited Medications

The use of following medications is prohibited. If it is considered necessary by the investigator, these medications will be tapered off and then stopped. If the dose of antidepressants is to be tapered, the subject should visit the trial site to confirm safety, where appropriate.

6.5.1.1 Fourteen Days Before Visit 2 Through Visit 11

• Monoamine oxidase inhibitors

6.5.1.2 Visit 2 Through Visit 9

- Antidepressants
- Benzodiazepines (except for ultrashort-acting hypnotics and sedatives)
- Drugs that are considered to affect the metabolic/activity systems of serotonin, noradrenaline, or dopamine
- Central nervous system drugs (except for ultrashort-acting hypnotics and sedatives; antipyretic, analgesic and anti-inflammatory agents; and general cold medicines)
- Chinese herbal medicines (drugs indicated for neurosis, anxiety neurosis, neurasthenia, and insomnia)
- Over the counter drugs used as sleeping pills
- Supplements used for improvement of depressive symptoms (St. John's wort, S-adenosylmethionine [SAM-e], ω-3 fatty acid, kava extract, γ-aminobutyric acid [GABA])
- Varenicline

6.5.1.3 Visit 2 Through Visit 10

Strong cytochrome P450 (CYP) 3A4 inhibitors, CYP1A2 inhibitors, CYP2D6 inhibitors, CYP3A4 inducers, CYP1A2 inducers, CYP2B6 inducers, and CYP2D6 substrates with narrow therapeutic range (except for topical drugs)

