4.2 Scientific Rationale for Trial Design

The trial was designed with reference to the Guideline for Clinical Evaluation of Antidepressants⁷ (hereinafter referred to as the Clinical Evaluation Guideline). The Clinical Evaluation Guideline states that "a double-blind, placebo-controlled comparison trial is necessary for evaluation of efficacy of antidepressants" and "duration of treatment in exploratory and confirmatory trials of antidepressants is generally 6 to 8 weeks." Therefore, this trial was designed as a randomized, double-blind, placebo-controlled, parallel-group comparison trial to appropriately assess the efficacy and safety with a 6-week double-blind treatment period.

The screening period was set as a necessary period to confirm the inclusion/exclusion criteria and wash out prior medications. The placebo lead-in period (single-blind with subjects blinded to treatment received) was set because it is preferable to exclude subjects with significant changes in symptoms for the purpose of appropriately evaluating the efficacy of OPC-64005. Although no AEs related to withdrawal symptoms have been reported after the end of administration of OPC-64005 in previous trials, the double-blind tapering period was set because when antidepressants are discontinued, a gradual reduction in dose is generally recommended. The post-treatment observation period was set to confirm the safety of subjects after administration of the final dose of OPC-64005.

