4.3.2 Rationale for Dose

The dose of OPC-64005 in this trial was determined based on estimated receptor occupancy of each monoamine transporter obtained from a simulation analysis⁸ of a PK/PD model, which was newly conducted using the results of the PET trials in healthy adults.⁹

There are many studies on intracerebral monoamine receptor occupancy of antidepressants, and PET trials 10,11,12 of various drugs reported that the ideal monoamine transporter occupancy by TRIs, taking antidepressant effect and safety into account, are $\geq 80\%$ for SERT, 50% to 70% for NET, and $\leq 30\%$ for DAT. 13

Table 4.3.2-1 shows the estimated maximum occupancy of each monoamine transporter by OPC-64005 in the steady-state after repeated administration of OPC-64005. The SERT occupancy reached approximately 70% at OPC-64005 10 mg. The NET occupancy was > 50% at OPC-64005 10 mg and > 60% at 20 mg. The DAT occupancy reached 25% at OPC-64005 20 mg. OPC-64005 is a TRI expected to be a new therapeutic option for depression. Since OPC-64005 is expected to act on serotonin, noradrenaline, and dopamine at 20 mg based on the estimated occupancy, 20 mg was selected as the dose for assessing efficacy and safety in this trial.

Table 4.3.2-1 Estimated Maximum Occupancy (Median) of Each Monoamine Transporter by OPC-64005 in Steady-state				
OPC-64005 Dose	5 mg	10 mg	20 mg	30 mg
SERT	64%	71%	74%	75%
NET	40%	55%	63%	66%
DAT	5%	12%	25%	34%

Estimated by a PK/PD model simulation based on the results of the PET trials (Trials 277-10-205, 277-13-001, and 277-14-001)

In the previous phase 1 repeated-dose trials in healthy adults (Trials 277-12-001 and 277-10-206), tolerability was confirmed at doses up to 30 mg/day. The overseas phase 2 trial in AD/HD patients (Trial 277-201-00001) confirmed that OPC-64005 was safe and tolerable when administered at 20 mg/day for 4 days, followed by a dose increased on

Day 5 to 30 mg/day, which was administered up until Day 56, for a total of 8 weeks. Based on these clinical results, it was judged that there are no significant safety problems in selecting 20 mg as the dose for efficacy assessment in the present trial.

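### The antidepressant ban ends at Visit 9 while the 20-mg group is dosed to Visit 10, and later medication recording and TEAE summaries cannot cleanly separate taper, post-dose and new-antidepressant effects

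*Protocol*

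**What the plan says.** **Medication windows (Protocol 6.5.1).** There are three end points.
- MAO inhibitors: "6.5.1.1 Fourteen Days Before Visit 2 Through Visit 11".
- Antidepressants, benzodiazepines, other CNS drugs and "Drugs that are considered to affect the metabolic/activity systems of serotonin, noradrenaline, or dopamine": "6.5.1.2 Visit 2 Through Visit 9".
- Strong CYP inhibitors, inducers and related substrates: "6.5.1.3 Visit 2 Through Visit 10".

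Protocol 6.5.3 discourages new medication but does not forbid it.

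**Dosing after Visit 9 (Protocol 6.1.1.3).** For the 20-mg group: "One placebo tablet and one OPC-64005 10-mg tablet will be administered orally once daily for 1 week". The 10-mg and placebo groups take placebo only. Under 6.1.1.4 the same regimens apply to subjects who discontinue after Visit 4 and taper.

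**Purpose of follow-up (Protocol 4.2).** "The post-treatment observation period was set to confirm the safety of subjects after administration of the final dose of OPC-64005". The taper itself is justified by general practice when antidepressants are stopped.

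**Recording (Protocol 6.5).** "The investigator will record all concomitant medications taken by the subject from 28 days prior to informed consent through Visit 10". After that, only drugs that treat or caused an adverse event are recorded.

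**Analysis.** SAP 9.2 tabulates TEAEs by day of first onset in weekly categories to Day 42, then one open category. SAP 9.7.2 gives C-SSRS results by time point and treatment group, including post-treatment observation. SAP 7.5 tabulates drugs used after the double-blind treatment period.

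**The concern.** From Visit 9 a site may start a new antidepressant without knowing whether the subject is still taking OPC-64005. An adverse event or C-SSRS finding after that visit could then come from the reduced dose, from stopping OPC-64005, or from the new drug.

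Starting an antidepressant happens after randomisation and plausibly depends on response, so the frequency of starts may differ between groups. If the drug works, start-up events could be commoner on placebo and hide a withdrawal effect; the opposite is also possible. The data needed to examine this are incomplete after Visit 10, and the TEAE summaries do not distinguish the periods.

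What is at stake is the reading of late safety data, in a trial that has safety among its objectives and is the first of this compound in MDD. The efficacy result is not at stake.

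**Working it through.** No design figure in the plan bears on this point. The check is a comparison of sections with visit-day arithmetic.

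**1. Overlap of dosing and the lifted ban.** Visit 9 is Day 43 ± 2 and Visit 10 is Day 50 ± 2 (Table 1.3-1).
- Nominal taper: 50 − 43 = 7 days.
- Shortest: (50 − 2) − (43 + 2) = 3 days. Longest: (50 + 2) − (43 − 2) = 11 days.

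In this interval the 20-mg group is on OPC-64005 and the 6.5.1.2 ban has ended. The CYP list still applies, as does the grapefruit restriction in 5.3.1, which runs to the end of tapering.

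**2. Length of the mixed period.** Visit 11 is 14 ± 7 days after Visit 10 or the final dose.
- Visit 10 to Visit 11: 14 days nominal, 7 to 21.
- Visit 9 to Visit 11, with Visits 9 and 10 on target: 7 + 14 = 21 days nominal, 14 to 28.

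**3. Recording.** In the last 14 nominal days only AE-linked drugs are captured. Protocol 8.8.2 counts worsening of the disease as an AE only when its features are unusual, severe or unexpected. An antidepressant started for ordinary persisting depression can therefore go unrecorded. The table in SAP 7.5 would combine one fully recorded week with about two partly recorded ones.

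**4. Early discontinuers.** Protocol 7.3.2 names the need for a disallowed treatment as a reason to stop, and 7.3.3 names lack of efficacy, so these subjects are plausible candidates for a new antidepressant. Under 1.4.7 those who taper go from the discontinuation examination to the Visit 10 examination and then Visit 11. They have no Visit 9, and nothing says which contact takes its place in 6.5.1.2. Those who do not taper go straight to Visit 11, so the Visit 10 recording limit is also undefined for them.

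**5. What the onset categories can separate.**
- A completer on schedule tapers on Days 43 to 49 and is observed from Day 50. Both periods fall in the category above Day 42.
- A subject who discontinues on Day 22 and starts the taper that day is dosed on Days 22 to 28 (22 + 7 − 1 = 28), with Visit 11 nominally on Day 42 (28 + 14). Taper events fall in the Day 22–28 category and post-dose events in Days 29–35 and 36–42, alongside other subjects' on-treatment events.

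Fixed study days therefore cannot isolate either period; each subject's own dosing dates can.

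**6. Primary endpoint.** SAP 3.4 excludes data from the day after taper dosing starts from every treatment-period time point. The Week 6 MADRS comparison is unaffected.

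**The case against.** The case against has real force, and most of it limits the point rather than removing it.

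- **A reader might infer that these periods cannot show anything about the safety of stopping.** The documents do not support that. Tapering stays blinded, the randomised placebo group is under the same medication rules, adverse events and C-SSRS are collected to Visit 11, and new drugs are discouraged. Nor is demonstrating freedom from withdrawal effects a stated objective.
- **A reader might infer that every group is still on drug, or that every serotonergic drug is allowed, after Visit 9.** Only the 20-mg group is still dosed. MAO inhibitors stay barred to Visit 11, and any antidepressant on the strong-CYP list stays barred to Visit 10.
- **Different end dates are not in themselves a contradiction.** Windows can differ by drug class, and Visit 9 is the last scheduled efficacy visit for completers. Amendment 1 moved the CYP list to Visit 10 for subject safety and left the antidepressant entry alone, which may have been deliberate. No reason is given, however, and the gap for early discontinuers remains.
- **Parts of a remedy exist.** C-SSRS is already shown by time point and group, drugs are fully recorded to Visit 10, and AE-linked drugs are recorded after that. What is missing is unlinked starts after Visit 10, a usable split of late TEAEs, and any flag for new antidepressant use.
- **Day counts and occupancy estimates do not measure bias.** Table 4.3.2-1 gives estimated maximum SERT occupancy of 71% on 10 mg and 74% on 20 mg, but DAT falls from 25% to 12%. These figures show that exposure continues in the taper week, not how many events are misattributed.

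**Conclusion.** The point holds as a limited one. The antidepressant and monoaminergic ban ends a nominal 7 days before OPC-64005 ends in the 20-mg group, and it has no stated end for early discontinuers who taper. Over a nominal 21 days after Visit 9, taper, post-dose and new-drug effects cannot be cleanly separated, and for about 14 of those days the medication record is incomplete by design.

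The size is given in days because the documents contain no rate of antidepressant starts and no expected number of late events; the number of events affected cannot be estimated from them. That starts may differ between groups is an assumption based on their likely dependence on response. The day counts assume visits on target and, for completers, a taper starting at Visit 9.

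The late safety comparison is weakened, not void, and the primary analysis stands. Which end date suits each drug class is a clinical decision on which this review takes no position.

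**What to change.** 1. **Protocol 6.5.1.1 to 6.5.1.3:** reconcile the end dates with the taper in 6.1.1.3 and 6.1.1.4, and state how they apply to early discontinuers. The sponsor's medical team decides which date applies.
2. **Protocol 6.5:** record the name and start date of every antidepressant or other psychotropic drug through Visit 11 in all subjects, including those with no Visit 10.
3. **SAP 9.2:** replace the open onset category with separate tapering-period and post-treatment TEAE summaries by treatment group, defined by each subject's own dosing dates.
4. **SAP 9.2 and 9.7.2:** flag adverse events and C-SSRS findings that occur after the first dose of a new antidepressant. Label this split as descriptive, because starting such a drug is a post-randomisation event and the subgroups are not randomised comparisons.

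The cost is a short amendment, one extra medication query at a visit already held, and one or two extra tables. No additional visits or subjects are needed.
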